2 INTRODUCTION

2.1 BACKGROUND

Akili Interactive's videogame-like digital treatment, AKL-T01™ (EVO™-Multi), is based on the work of UCSF [name], MD, who has identified a way to measure and improve the ability to process interference events (essentially, interruptions and distractions). Interference susceptibility is recognized as a limiting factor across global executive function (including attention and memory) and is known to be fragile in multiple diseases. [name] work also demonstrated that changes in EEG signals occurred at neurological loci associated with cognitive control. The basic scientific mechanisms underlying AKL-T01 have been tested in controlled (N=203) studies of healthy participants across a wide age range (8 to 70 years of age) to validate the ability to detect differences between age groups and to enhance interference processing in older adults. AKL-T01 was tested in a, follow-on, controlled (N=80) study of ADHD children and age-matched neurotypical controls to validate its ability to detect differences between the groups and to provide insight into AKL-T01 as a therapeutic product. Findings provide preliminary support that this digital treatment may improve attention, working memory, and inhibition in children with ADHD. The pivotal study STARS-ADHD; a multi-center, randomized, double-blind, active-controlled study of AKL-T01 in 348 pediatric subjects ages 8-12 with ADHD demonstrated a statistically significant improvement ($p=0.006$) between AKL-T01 and an active control on the primary endpoint (TOVA API change from Baseline to Post-Treatment) (STARS-ADHD, in progress).

Most relevant to this protocol is a published feasibility study of pediatric Sensory Processing Dysfunction (SPD) at the University of California, San Francisco (UCSF), which requested that 57 children ages 8 to 12 (24 Neurotypical, 20 SPD with inattention, and 13 SPD without inattention) to engage with AKL-T01 treatment at home for 30 minutes per day, 5 days per week for 4 weeks. Participants were assessed using EEG, TOVA and the Vanderbilt Inattention scale (parent-reported) at Baseline/Day 0 and at Exit/Day 28. All children showed statistically significant improvement in attention as measured by TOVA. Children with SPD and with inattention also showed statistically significant enhancement of Mid-Frontal Cortex Theta power as measured by EEG while neurotypical and SPD children without inattention did not.

2.2 STUDY RATIONALE

Previous work has been done to establish the effect of AKL-T01 on MFT activity in children with SPD and inattention according to the Vanderbilt ADHD Diagnostic Parent Rating Scale, however no work has been done to study the effect of MFT activity in children with a confirmed diagnosis of ADHD.

2.3 RISK/BENEFIT ASSESSMENT

2.3.1 KNOWN POTENTIAL RISKS

The risks to the participants in this study are very small. The study involves completing some computerized tests, game-based digital therapies, and answering some questions. It is possible that the participant could become frustrated or fatigued by some of the tasks.

The participant may also experience dizziness, headaches, nausea, decreased frustration tolerance, or emotional reaction as a result of playing the study device. If the participant becomes frustrated or

fatigued, they may stop at any time. There are no other risks to taking part in this study of which we are aware.

2.3.2 KNOWN POTENTIAL BENEFITS

Based on preliminary data obtained in several studies, including a feasibility study of AKL-T01 in pediatric SPD subjects, the potential benefits of the AKL-T01 game-based treatment for this population may include improvements in midline frontal theta activity and/or parental report of inattention. Given the central role of attention in the pathophysiology of ADHD, this benefit is substantial.

2.3.3 ASSESSMENT OF POTENTIAL RISKS AND BENEFITS

To date, there have been no serious adverse events reported across several studies with the device. The risk/benefit ratio for use is favorable.

3 OBJECTIVES AND ENDPOINTS

OBJECTIVES	ENDPOINTS
Primary	
Demonstrate enhancement of MFT power measured by stimulus-locked EEG (Perceptual Discrimination Task (PDT)=Stimulus) in children with ADHD following 4 weeks of at-home AKL-T01 treatment.	Change in midline frontal theta power as measured by PDT-locked EEG.
Secondary	
Demonstrate normalized MFT power in children with ADHD following 4 weeks of at-home AKL-T01 treatment.	MFT power of ADHD cohort at Day 28 compared to that of neurotypical cohort at Day 0 (historical controls).
Exploratory	
Demonstrate improvement in attention in children with ADHD following 4 weeks of at-home AKL-T01 treatment.	
Reaction time and reaction time variability as measured by TOVA.Reaction time and reaction time variability as measured by perceptual discrimination task.Reaction time and reaction time variability as measured by ALK-M01 Assessment.

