1 PROTOCOL SUMMARY

1.1 SYNOPSIS

Title:	A study to assess Midline Frontal Theta (MFT) power as measured by stimulus-locked electroencephalography (EEG) before and after AKL-T01 treatment for improving attention in pediatric participants ages 8-12 years old with Attention Deficit Hyperactivity Disorder (ADHD)
Hypothesis:	ADHD children receiving 4 weeks of AKL-T01 treatment will show enhancement in MFT activity as measured by stimulus-locked EEG.
Objectives:	
Primary Objective:
 
• Demonstrate enhancement of MFT power measured by stimulus-locked EEG (Perceptual Discrimination Task (PDT)=Stimulus) in children with ADHD following 4 weeks of at-home AKL-T01 treatment. 
Secondary Objective:
 
• Demonstrate normalized MFT power in children with ADHD following 4 weeks of at-home AKL-T01 treatment. 
Exploratory Objectives:
 
• Demonstrate improvement in sustained attention by direct assessment in children with ADHD following 4 weeks of at-home AKL-T01 treatment.• Demonstrate improvement in ADHD symptoms by parent report in children with ADHD following 4 weeks of at-home AKL-T01 treatment.
Endpoints:	
Primary Endpoint:
 
• PDT-locked EEG relative to pre-training 
Secondary Endpoint:
 
• PDT-locked EEG relative to a normative control cohort 
Exploratory Endpoints:
 
• Project EVO Assessment• Test of Variables of Attention (TOVA)• Vanderbilt Assessment
Study Population:	30 children ages 8 to 12 with ADHD from the United States
Description of Study Intervention:	AKL-T01 is a digital therapeutic software for the treatment of attention and inhibitory control deficits in patients with ADHD. AKL-T01 is an investigational medical device known as Software as a Medical Device (SaMD).
Study Duration:	From beginning of enrollment to last subject last visit, 12 months
Participant Duration:	29 Days

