9 STATISTICAL CONSIDERATIONS

9.1 STATISTICAL HYPOTHESES

OBJECTIVE	HYPOTHESIS
Primary	Children with ADHD, following 4 weeks of digital treatment with AKL-T01, will demonstrate enhancement of MFT power as measured by stimulus-locked EEG.
Secondary	Children with ADHD, following 4 weeks of digital treatment with AKL-T01, will demonstrate normalized MFT power as compared with a neurotypical population.

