9.2 POPULATIONS FOR ANALYSES

There will be two populations for analysis in this study.

The AKL-T01 Intervention Population will complete 28 days of AKL-T01 digital treatment. This population will enroll pediatric ADHD participants according to the inclusion criteria outlined in section 5.1 of this protocol. Only participants completing at least 50% of the prescribed treatment (i.e. 50 sessions) will be included in the analysis.

The neurotypical control group will also be analyzed as historical controls. This population was enrolled in *A pilot study to determine the feasibility of enhancing cognitive abilities in children with sensory processing dysfunction* (Anguera, 2017).

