9.3 STATISTICAL ANALYSES

All statistical analyses will be conducted using SPSS 22.0 (SPSS Inc.). Group effects for both behavioral and neural measures will be assessed with separate ANOVAs and ANCOVAs with planned follow-up contrasts (Fisher's LSD). The ANCOVA approach is considered to be a more suitable approach when post-test performance that is not conditional / predictable based on pre-test performance is the primary outcome of interest following treatment, as opposed to characterizing gains achieved from pre-training performance (for example, group X session interaction(s)). However, both are appropriate statistical approaches that have been used to assess cognitive training outcomes. Thus, our approach will be to present the p-values for each approach. Planned follow-up contrasts will be used to directly assess changes within each group. To minimize influential data points, we will remove values +/- 2 standard deviations for all group analyses. For correlations tested, we will use a more stringent outlier removal procedure (Cook's D> 1) given the smaller cohort size and possible inflated change scores.

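### The secondary objective is to demonstrate normalized MFT power, but the plan sets no criterion for it and names only difference tests, which cannot support the claim

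*Combined protocol and SAP*

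**What the plan says.** - **Objective and hypothesis.** The Synopsis (1.1) and Section 3 set out to demonstrate normalized MFT power after treatment. Section 9.1 restates this as the hypothesis: children with ADHD "will demonstrate normalized MFT power as compared with a neurotypical population". No null or alternative is given.
- **Endpoint.** Section 3: "MFT power of ADHD cohort at Day 28 compared to that of neurotypical cohort at Day 0 (historical controls"). The Synopsis has only "PDT-locked EEG relative to a normative control cohort".
- **Methods.** Section 9.3 names ANOVAs and ANCOVAs with planned Fisher's LSD contrasts, and describes the planned contrasts as assessing change within each group. On the choice between the two models it says "Thus, our approach will be to present the p-values for each approach". It adds that "we will remove values +/- 2 standard deviations for all group analyses".
- **Analysis set.** Section 9.2: "Only participants completing at least 50% of the prescribed treatment (i.e. 50 sessions) will be included in the analysis". The same section takes the neurotypical controls from an earlier pilot study in sensory processing dysfunction (SPD).
- **Size and timing of the control data.** Section 2.1 describes an SPD feasibility study that asked "57 children ages 8 to 12 (24 Neurotypical, 20 SPD with inattention, and 13 SPD without inattention) to engage with AKL-T01 treatment at home". It continues: "Participants were assessed using EEG, TOVA and the Vanderbilt Inattention scale (parent-reported) at Baseline/Day 0 and at Exit/Day 28".

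**The concern.** Normalization is a claim of similarity: the treated ADHD children are now like neurotypical children, or at least no lower. A test of difference is built for the opposite claim. If it finds a significant deficit at Day 28, that counts against normalization. If it finds nothing, the result fits both true similarity and a moderate deficit that the sample was too small to detect. The plan does not say that non-significance will be read as normalization, but it offers no other basis for the positive conclusion and does not rule that reading out. The smaller or noisier the sample, the easier such a conclusion would be to reach.

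There is a second gap. To normalize implies a deficit to begin with, and no ADHD versus neurotypical contrast at Day 0 is listed as an endpoint or named as a contrast. The cohorts might not differ at Day 0, and the plan could still end with a statement that MFT power was normalized.

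**Working it through.** The plan states no alpha, power, SD, effect size or margin for this objective, so there is no figure of its own to reproduce. The calculations below only show how large the problem could be.

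**Inputs**
- ADHD children: 30 (Synopsis).
- Neurotypical controls: 24 (Section 2.1). This takes the feasibility study described there to be the control source named in Section 9.2. The number with usable EEG is not stated.
- Assumed: two-sided 0.05, equal SDs, gaps in SD units, and a two-sample t-test in place of the named models.
- Assumed for a smaller analysis set: 20 ADHD children left after the 50% completion rule. The plan gives no figure.

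**Precision**

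SE = √(1/n₁ + 1/n₂), and the 95% CI half-width is t(0.975, n₁+n₂−2) × SE.
- 30 vs 24: SE = √(0.0333 + 0.0417) = 0.274; half-width = 2.007 × 0.274 = 0.55 SD.
- 20 vs 24: SE = √(0.0500 + 0.0417) = 0.303; half-width = 2.018 × 0.303 = 0.61 SD.

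**Chance that a true remaining deficit is non-significant**

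Noncentral t with noncentrality d/SE (for example 0.5/0.274 = 1.83 at 30 vs 24):

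| True deficit | 30 vs 24 | 20 vs 24 |
|---|---|---|
| 0.3 SD | 81.1% | 83.8% |
| 0.5 SD | 56.7% | 63.5% |
| 0.8 SD | 18.2% | 26.7% |

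A deficit must be about 0.78 SD (30 vs 24) or 0.87 SD (20 vs 24) to be detected with 80% power.

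**Effect of the 2-SD removal**

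Section 9.3 does not say whether values are removed within each group or across both. Simulation at 30 vs 24 with normal data, one pass, 200,000 runs:
- Within group: non-significance at 0.3, 0.5 and 0.8 SD is 74%, 50% and 16%, but coverage of the 95% CI falls to about 90%.
- Across the pooled children: 84%, 65% and 28%. A true 0.5 SD gap shrinks to about 0.40 SD on average, and coverage at that gap is 92%.

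Either way, the trimmed interval is not a sound basis for judging the remaining gap.

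**Could a margin rule work at this size?**

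Simulation at 30 vs 24, untrimmed, 400,000 runs. The two-sided rule needs the 90% CI inside ± margin. The one-sided rule needs the one-sided 95% lower bound above minus the margin.

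| True gap | Margin | Two-sided rule passes | One-sided rule passes |
|---|---|---|---|
| 0 | 0.5 SD | 14% | 56% |
| 0 | 0.8 SD | 78% | 89% |
| 0.5 SD deficit | 0.8 SD | 28% | about 28% |

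A margin of 0.5 SD is poorly powered. A margin of 0.8 SD has reasonable power but would call a true 0.5 SD deficit normalized more than a quarter of the time.

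**The case against.** The strongest reply is that this is a gap in definition, not a stated invalid inference. The plan never says that p > 0.05 means normalized, and the p-value sentence in Section 9.3 settles whether to report ANOVA or ANCOVA; it does not exclude estimates or intervals. That is fair as a reading of the sentence. No estimate or interval is specified, however, and no rule connects any result to the claim.

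On Day 0, Section 9.3 covers group effects on neural measures and mentions group-by-session interactions as an example, so a model using both cohorts' Day 0 data is possible. This stands: the contrast could be run. It is still not named, and the contrasts that are described are within-group.

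Section 2.1 says only that the earlier children had EEG, not that it was locked to the perceptual discrimination task, so the comparability of the control data is partly assumed. The plan's own secondary endpoint relies on the same assumption at Day 0. An analysis using neurotypical Day 28 data would go further than the current endpoint.

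The 2-SD removal is a wider issue that would remain even if normalized were well defined. It matters here because it changes the estimate and interval on which a corrected analysis would rest.

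Finally, this is a secondary objective in a single-arm, open-label pilot, and the primary within-child question is unaffected. That limits the consequence. It does not supply a definition, and a small sample is where non-significance misleads most.

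**Conclusion.** The concern holds and should be fixed. Followed as written, the plan can produce evidence against normalization but cannot validly support the conclusion that its secondary objective sets out to demonstrate. That follows from the text and does not depend on any calculation.

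The calculations give the scale: at 30 vs 24 without trimming, a moderate remaining deficit of 0.5 SD would go undetected more often than not, and fewer analysed children would make this worse. They rest on two-sided 0.05, equal SDs, 24 usable controls and a simple two-group comparison, none of which the plan confirms. The 20-child scenario is purely illustrative.

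**What to change.** 1. Pre-specify the ADHD versus neurotypical contrast at Day 0, to show whether there is a deficit to normalize.
2. Report ADHD Day 28 minus neurotypical Day 0 as the remaining gap with a 95% CI, calculated without the 2-SD removal, with the trimmed version as a sensitivity analysis. State that a non-significant p-value will not be called normalization.
3. Keep the word *normalized* only if the sponsor first states its direction (two-sided equivalence, or at least the neurotypical level) and fixes a justified margin before analysis, to be met by the matching interval rule. Otherwise reword the objective as descriptive. Given the power at this sample size, the descriptive report in item 2 is the realistic option.
4. Optionally, add ADHD Day 28 versus neurotypical Day 28 as a sensitivity analysis for a retest shift of unknown size, noting that those neurotypical children were also asked to use AKL-T01. This depends on their Day 28 EEG being available in comparable form.

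Items 1 to 3 cost a few sentences and use EEG that the documents describe as collected or planned. The downside is that the normalization claim becomes harder to make, and the secondary result would probably be reported as an estimated gap.

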5 STUDY POPULATION

5.1 INCLUSION CRITERIA

In order to be eligible to participate in this study, an individual must meet all of the following criteria:

1. Age 8 to 12 at the time of parental informed consent
2. Male or female
3. Confirmed ADHD diagnosis at screening/baseline visit based on DSM-V criteria and established via the MINI-KID administered by a trained clinician either in person or via teleconference
4. WISC V FSIQ ≥ 70
5. Vanderbilt ADHD Diagnostic Parent Rating Scale: Must score a 2 or 3 on at least 6 items 1-9 AND must score a 4 on at least 2, or 5 on at least 1, of items 48-54 (performance questions).
6. Consistently off stimulant medication for ≥ 1 week. OR currently on stimulant medication and agree to stop taking the medication for a 1 week prior to the baseline visit and off through duration of training and post-training assessment (note: participants will only be allowed to washout of stimulant medication if in the opinion of the investigator they are currently inadequately managed on their medication and it is appropriate to stop taking their medication for the duration of the trial)
7. Consistently off Psychotropic drug for ≥ 1 month
8. Consistently off non-stimulant medication for ADHD (e.g. atomoxetine, clonidine, guanfacine) for ≥ 1 month

9. Able to follow written and verbal instructions (English) as assessed by the PI and/or study coordinator
10. Functioning at an age-appropriate level intellectually
11. Able to comply with all testing and requirements

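### The secondary ADHD-versus-neurotypical MFT comparison specifies no matching on, or adjustment for, age or sex, so a difference in recruitment mix can bias it either way, including towards an apparent normalization

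*Combined protocol and SAP*

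**What the plan says.** Section 3 (Objectives and Endpoints) defines the secondary endpoint as "MFT power of ADHD cohort at Day 28 compared to that of neurotypical cohort at Day 0 (historical controls". Section 9.2 confirms the source: "The neurotypical control group will also be analyzed as historical controls", enrolled in an earlier feasibility study in sensory processing dysfunction (SPD). Section 2.1 describes what appears to be that study as "57 children ages 8 to 12 (24 Neurotypical, 20 SPD with inattention, and 13 SPD without inattention". That the two sections mean the same study is inferred from the matching description.

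The synopsis plans "30 children ages 8 to 12 with ADHD from the United States". Section 5.1 admits "Age 8 to 12 at the time of parental informed consent" and "Male or female", with no quota or stratification on either.

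On analysis, section 9.3 says "Group effects for both behavioral and neural measures will be assessed with separate ANOVAs and ANCOVAs". It lists no covariates; its discussion of ANCOVA implies only the pre-test score. The Schedule of Activities collects demographics, but no section assigns them a place in an analysis. The phrase "controlled (N=80) study of ADHD children and age-matched neurotypical controls" in section 2.1 belongs to a different, earlier study and says nothing about how the present controls were chosen.

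**The concern.** This is a non-randomised contrast between cohorts recruited at different times for different purposes. A common 8-to-12 range caps the possible age gap. It does not balance age within the range, and it does nothing for sex. If MFT power varies with age or sex and the mixes differ, part of the observed difference is not due to ADHD or to treatment.

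The bias can go either way. It can create an apparent remaining deficit, or it can hide a real one. The second error matters more here, because the objective is to show normalized MFT power and a hidden deficit favours that reading.

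The implied pre-test covariate does not help. For the controls, the value being compared is the Day 0 value, so no separate earlier score exists to adjust for. This is the only secondary objective, and it rests wholly on this contrast.

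**Working it through.** The plan gives no power, alpha, SD or age slope for this comparison, so there is no figure of its own to reproduce. What follows is an illustration in units of the within-cohort SD.

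**Inputs from the documents.** 30 ADHD children (synopsis) and 24 neurotypical children (section 2.1).

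**Assumptions, not in the documents.** Two-sided 5% test; MFT power changes by 0.1-0.3 SD per year of age; recruitment produces a systematic mean-age gap of 0.5-1.0 year.

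**Precision.** SE = sqrt(1/30 + 1/24) = 0.274 SD. With 30 + 24 - 2 = 52 degrees of freedom, t(0.975) = 2.007, so the 95% CI half-width is 2.007 x 0.274 = 0.55 SD.

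**Bias.** Bias = slope x age gap. Lowest: 0.1 x 0.5 = 0.05 SD. Highest: 0.3 x 1.0 = 0.30 SD.

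**No true difference.** Rejection rate from the noncentral t with noncentrality bias/SE:

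| Bias (SD) | Rejection rate |
|---|---|
| 0.05 | 5.4% |
| 0.10 | 6.5% |
| 0.15 | 8.4% |
| 0.20 | 11.1% |
| 0.30 | 18.9% |

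**True deficit of 0.5 SD (assumed), partly hidden.** The apparent deficit is 0.5 minus the bias:

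| Bias (SD) | Apparent deficit (SD) | Power |
|---|---|---|
| 0 | 0.50 | 43% |
| 0.20 | 0.30 | 19% |
| 0.30 | 0.20 | 11% |

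**Sex.** The bias is the sex difference in the outcome times the difference in sex proportion. Assuming a 0.2-0.4 SD sex difference and a 20-30 percentage-point imbalance, it runs from 0.2 x 0.2 = 0.04 SD to 0.4 x 0.3 = 0.12 SD.

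**Chance imbalance, checked separately.** Both cohorts were simulated from one age distribution (uniform from 8 to 13, assumed) with no group effect. At slopes of 0.1, 0.2 and 0.3 SD per year the unadjusted test rejected 4.9%, 5.0% and 5.0% of the time. A mean-age gap above 0.5 year arose in about 20% of draws, and above 1.0 year in about 1%. The age variation is already in the within-group SD, so the unconditional error rate stays nominal. The inflated rates in the first table need a systematic recruitment difference, or are conditional on a gap that has occurred.

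**The case against.** The strongest reply is that every bias input is assumed. No section gives either cohort's mean age or sex mix, or says that MFT power varies with age or sex between 8 and 12. The programme studies that compared age groups spanned 8 to 70 years, which says little about a slope inside this range, and age matching in the earlier N=80 study is not evidence of imbalance here. That stands: size and direction are unknown, and the low end (5.4% against 5%) is negligible.

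A reader might infer three stronger things that the documents do not support.

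- That chance imbalance with 30 and 24 children inflates the false-positive rate. It does not, as the simulation shows.
- That the controls are known to be unmatched, or that age is ruled out of the ANCOVA. Both rest on silence; the correct word is unspecified.
- That the reaction-time endpoints share the problem. Section 9.3 mentions behavioral group effects, but the exploratory endpoints in section 3 name no neurotypical comparison. They are affected only if one is run.

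It is also fair that this is a single-arm pilot, that the primary endpoint is a within-child change untouched by this issue, and that the assumed bias lies inside the 0.55 SD half-width. Adjustment alone would not make normalization demonstrable, because section 9.1 gives no margin or decision rule.

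What the reply does not remove is the gap. An ANCOVA with unlisted covariates leaves the choice of age and sex open until the data are seen.

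**Conclusion.** The point holds for the secondary MFT comparison. Two separately recruited cohorts are contrasted with no stated matching or age/sex adjustment, and the implied pre-test covariate cannot adjust this contrast. A systematic difference in age or sex mix would bias the result in a direction that cannot be known from the documents.

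The quantified range depends on the assumed slopes, the assumed age gap, a two-sided 5% test and the full 30 and 24 children. The documents do not show that an imbalance exists, so the conclusion is that bias is possible and unguarded, not that it is present. The change is worth making because it is cheap and the secondary objective has no other support. It does not bear on the primary endpoint.

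**What to change.** For the secondary MFT comparison, and for any behavioral comparison actually run against the neurotypical cohort, prespecify outcome ~ group + age at test (continuous) + sex. Report the adjusted group difference with its 95% CI as the secondary result, with the unadjusted difference beside it. Table age and sex by cohort. If the age effect is linear and correctly modelled, this removes the age bias. Under chance imbalance alone it still removes the realised imbalance and may add precision.

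The cost is SAP wording and two of about 52 degrees of freedom. Fewer are available once the 50% compliance rule (section 9.2) and the 2-SD removal (section 9.3) reduce the numbers. The historical cohort's age and sex must be obtainable from its dataset, which the documents do not establish. No new visits or participants are needed. Adjustment does not remove other differences between historical and current cohorts.
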